7.2.2 Reporting of Pregnancy and Lactation to the Sponsor

Although pregnancy and lactation are not considered adverse events, it is the responsibility of investigators or their designees to report any pregnancy or lactation in a subject (spontaneously reported to them) that occurs during the trial.

Pregnancies and lactations that occur after the consent form is signed but before treatment allocation/randomization must be reported by the investigator if they cause the subject to be excluded from the trial, or are the result of a protocol-specified intervention, including but not limited to washout or discontinuation of usual therapy, diet, placebo treatment or a procedure. Pregnancies and lactations that occur from the time of treatment allocation/randomization through 120 days following cessation of Sponsor's product, or 30 days following cessation of treatment if the subject initiates new anticancer therapy, whichever is earlier, must be reported by the investigator. All reported pregnancies must be followed to the completion/termination of the pregnancy. Pregnancy outcomes of spontaneous abortion, missed abortion, benign hydatidiform mole, blighted ovum, fetal death, intrauterine death, miscarriage and stillbirth must be reported as serious events (Important Medical Events). If the pregnancy continues to term, the outcome (health of infant) must also be reported.

Such events must be reported within 24 hours to the Sponsor either by electronic media or paper. Electronic reporting procedures can be found in the EDC data entry guidelines. Paper reporting procedures can be found in the Investigator Trial File Binder (or equivalent).

7.2.3 Immediate Reporting of Adverse Events to the Sponsor

7.2.3.1 Serious Adverse Events

A serious adverse event is any adverse event occurring at any dose or during any use of Sponsor's product that:

- Results in death;
- Is life threatening;
- Results in persistent or significant disability/incapacity;
- Results in or prolongs an existing inpatient hospitalization;
- Is a congenital anomaly/birth defect;
- Is an other important medical event.

Note: In addition to the above criteria, adverse events meeting either of the below criteria, although not serious per ICH definition, are reportable to the Sponsor in the same timeframe as SAEs to meet certain local requirements. Therefore, these events are considered serious by the Sponsor for collection purposes.

- Is a new cancer (that is not a condition of the study);
- Is associated with an overdose.

Refer to [Table 7](#) for additional details regarding each of the above criteria.

For the time period beginning when the consent form is signed until treatment allocation/randomization, any serious adverse event, or follow up to a serious adverse event, including death due to any cause other than progression of the cancer under study (reference Section 7.2.3.3 for additional details), that occurs to any subject must be reported within 24 hours to the Sponsor if it causes the subject to be excluded from the trial, or is the result of a protocol-specified intervention, including but not limited to washout or discontinuation of usual therapy, diet, placebo treatment or a procedure.

For the time period beginning at treatment allocation/randomization through 90 days following cessation of treatment, or 30 days following cessation of treatment if the subject initiates new anticancer therapy, whichever is earlier, any serious adverse event, or follow up to a serious adverse event, including death due to any cause other than progression of the cancer under study (reference Section 7.2.3.3 for additional details), whether or not related to the Sponsor's product, must be reported within 24 hours to the Sponsor either by electronic media or paper. Electronic reporting procedures can be found in the EDC data entry guidelines. Paper reporting procedures can be found in the Investigator Trial File Binder (or equivalent).

Additionally, any serious adverse event, considered by an investigator who is a qualified physician to be related to the Sponsor's product that is brought to the attention of the investigator at any time following consent through the end of the specified safety follow-up period specified in the paragraph above, or at any time outside of the time period specified in the previous paragraph also must be reported immediately to the Sponsor.

All subjects with serious adverse events must be followed up for outcome.

7.2.3.2 Events of Clinical Interest

Selected non-serious and serious adverse events are also known as Events of Clinical Interest (ECI) and must be reported to the Sponsor.

For the time period beginning when the consent form is signed until treatment allocation/randomization, any ECI, or follow up to an ECI, that occurs to any subject must be reported within 24 hours to the Sponsor if it causes the subject to be excluded from the trial, or is the result of a protocol-specified intervention, including but not limited to washout or discontinuation of usual therapy, diet, placebo treatment or a procedure.

For the time period beginning at treatment allocation/randomization through 30 days following cessation of treatment, any ECI, or follow up to an ECI, whether or not related to the Sponsor's product, must be reported within 24 hours to the Sponsor, either by electronic media or paper. Electronic reporting procedures can be found in the EDC data entry guidelines. Paper reporting procedures can be found in the Investigator Trial File Binder (or equivalent).

Events of clinical interest for this trial include:

1. an overdose of Sponsor's product, as defined in Section 7.2.1 - Definition of an Overdose for This Protocol and Reporting of Overdose to the Sponsor, that is not associated with clinical symptoms or abnormal laboratory results.
2. an elevated AST or ALT lab value that is greater than or equal to 3X the upper limit of normal and an elevated total bilirubin lab value that is greater than or equal to 2X the upper limit of normal and, at the same time, an alkaline phosphatase lab value that is less than 2X the upper limit of normal, as determined by way of protocol-specified laboratory testing or unscheduled laboratory testing.*

*Note: These criteria are based upon available regulatory guidance documents. The purpose of the criteria is to specify a threshold of abnormal hepatic tests that may require an additional evaluation for an underlying etiology. The trial site guidance for assessment

and follow up of these criteria can be found in the Investigator Trial File Binder (or equivalent).

7.2.3.3 Protocol-Specific Exceptions to Serious Adverse Event Reporting

Efficacy endpoints as outlined will not be reported to the Sponsor, as described in Section 7.2.3. - Immediate Reporting of Adverse Events to the Sponsor.

Specifically, the suspected/actual events covered in this exception include any event that is disease progression of the cancer under study.

The Sponsor will monitor safety data to ensure the safety of the subjects in the trial. Any suspected endpoint which upon review is not progression of the cancer under study will be forwarded to global safety as a SAE within 24 hours of determination that the event is not progression of the cancer under study.

7.2.4 Evaluating Adverse Events

An investigator who is a qualified physician will evaluate all adverse events according to the NCI Common Terminology for Adverse Events (CTCAE), version 4.0. Any adverse event which changes CTCAE grade over the course of a given episode will have each change of grade recorded on the adverse event case report forms/worksheets.

All adverse events regardless of CTCAE grade must also be evaluated for seriousness.

Table 7 Evaluating Adverse Events

An investigator who is a qualified physician, will evaluate all adverse events as to:

V4.0 CTCAE Grading	Grade 1	Mild; asymptomatic or mild symptoms; clinical or diagnostic observations only; intervention not indicated.
	Grade 2	Moderate; minimal, local or noninvasive intervention indicated; limiting age-appropriate instrumental ADL.
	Grade 3	Severe or medically significant but not immediately life-threatening; hospitalization or prolongation or hospitalization indicated; disabling; limiting self-care ADL.
	Grade 4	Life threatening consequences; urgent intervention indicated.
	Grade 5	Death related to AE
Seriousness	A serious adverse event is any adverse event occurring at any dose or during any use of Sponsor's product that:	
	†Results in death; or	
	†Is life threatening; or places the subject, in the view of the investigator, at immediate risk of death from the event as it occurred (Note: This does not include an adverse event that, had it occurred in a more severe form, might have caused death.); or	
	†Results in a persistent or significant disability/incapacity (substantial disruption of one's ability to conduct normal life functions); or	
	†Results in or prolongs an existing inpatient hospitalization (hospitalization is defined as an inpatient admission, regardless of length of stay, even if the hospitalization is a precautionary measure for continued observation. (Note: Hospitalization for an elective procedure to treat a pre-existing condition that has not worsened is not a serious adverse event. A pre-existing condition is a clinical condition that is diagnosed prior to the use of a Merck product and is documented in the patient's medical history.); or	
	†Is a congenital anomaly/birth defect (in offspring of subject taking the product regardless of time to diagnosis); or	
	Is a new cancer (that is not a condition of the study) (although not serious per ICH definition, is reportable to the Sponsor within 24 hours to meet certain local requirements); or	
	Is an overdose (whether accidental or intentional). Any adverse event associated with an overdose is considered a serious adverse event for collection purposes. An overdose that is not associated with an adverse event is considered a non-serious event of clinical interest and must be reported within 24 hours.	
	Other important medical events that may not result in death, not be life threatening, or not require hospitalization may be considered a serious adverse event when, based upon appropriate medical judgment, the event may jeopardize the subject and may require medical or surgical intervention to prevent one of the outcomes listed previously (designated above by a †).	
Duration	Record the start and stop dates of the adverse event. If less than 1 day, indicate the appropriate length of time and units	
Action taken	Did the adverse event cause the Sponsor's product to be discontinued?	
Relationship to Sponsor's Product	Did the Sponsor's product cause the adverse event? The determination of the likelihood that the Sponsor's product caused the adverse event will be provided by an investigator who is a qualified physician. The investigator's signed/dated initials on the source document or worksheet that supports the causality noted on the AE form, ensures that a medically qualified assessment of causality was done. This initialed document must be retained for the required regulatory time frame. The criteria below are intended as reference guidelines to assist the investigator in assessing the likelihood of a relationship between the test drug and the adverse event based upon the available information. The following components are to be used to assess the relationship between the Sponsor's product and the AE; the greater the correlation with the components and their respective elements (in number and/or intensity), the more likely the Sponsor's product caused the adverse event (AE):	
	Exposure	Is there evidence that the subject was actually exposed to the Sponsor's product such as: reliable history, acceptable compliance assessment (pill count, diary, etc.), expected pharmacologic effect, or measurement of drug/metabolite in bodily specimen?
	Time Course	Did the AE follow in a reasonable temporal sequence from administration of the Sponsor's product? Is the time of onset of the AE compatible with a drug-induced effect (applies to trials with investigational medicinal product)?
	Likely Cause	Is the AE not reasonably explained by another etiology such as underlying disease, other drug(s)/vaccine(s), or other host or environmental factors

Relationship to Sponsor's Product (continued)	The following components are to be used to assess the relationship between the test drug and the AE: (continued)	
	Dechallenge	Was the Sponsor's product discontinued or dose/exposure/frequency reduced? If yes, did the AE resolve or improve? If yes, this is a positive dechallenge. If no, this is a negative dechallenge. (Note: This criterion is not applicable if: (1) the AE resulted in death or permanent disability; (2) the AE resolved/improved despite continuation of the Sponsor's product; or (3) the trial is a single-dose drug trial); or (4) Sponsor's product(s) is/are only used one time.)
	Rechallenge	Was the subject re-exposed to the Sponsor's product in this study? If yes, did the AE recur or worsen? If yes, this is a positive rechallenge. If no, this is a negative rechallenge. (Note: This criterion is not applicable if: (1) the initial AE resulted in death or permanent disability, or (2) the trial is a single-dose drug trial); or (3) Sponsor's product(s) is/are used only one time). NOTE: IF A RECHALLENGE IS PLANNED FOR AN ADVERSE EVENT WHICH WAS SERIOUS AND WHICH MAY HAVE BEEN CAUSED BY THE SPONSOR'S PRODUCT, OR IF REEXPOSURE TO THE SPONSOR'S PRODUCT POSES ADDITIONAL POTENTIAL SIGNIFICANT RISK TO THE SUBJECT, THEN THE RECHALLENGE MUST BE APPROVED IN ADVANCE BY THE SPONSOR CLINICAL DIRECTOR AS PER DOSE MODIFICATION GUIDELINES IN THE PROTOCOL.
		The assessment of relationship will be reported on the case report forms /worksheets by an investigator who is a qualified physician according to his/her best clinical judgment, including consideration of the above elements.
Record one of the following		Use the following scale of criteria as guidance (not all criteria must be present to be indicative of a Sponsor's product relationship).
Yes, there is a reasonable possibility of Sponsor's product relationship.		There is evidence of exposure to the Sponsor's product. The temporal sequence of the AE onset relative to the administration of the Sponsor's product is reasonable. The AE is more likely explained by the Sponsor's product than by another cause.
No, there is not a reasonable possibility of Sponsor's product relationship		Subject did not receive the Sponsor's product OR temporal sequence of the AE onset relative to administration of the Sponsor's product is not reasonable OR the AE is more likely explained by another cause than the Sponsor's product. (Also entered for a subject with overdose without an associated AE.)

7.2.5 Sponsor Responsibility for Reporting Adverse Events

All Adverse Events will be reported to regulatory authorities, IRB/IECs and investigators in accordance with all applicable global laws and regulations, i.e., per ICH Topic E6 (R1) Guidelines for Good Clinical Practice.

7.3 Trial Governance and Oversight

This trial was developed in collaboration with both Sponsor and non-Sponsor scientific experts who provide input with respect to the trial design, interpretation of trial results and subsequent peer-reviewed scientific publications.

8.0 STATISTICAL ANALYSIS PLAN

This section outlines the statistical analysis strategy and procedures for the study. If, after the study has begun, but prior to any final database lock, changes made to primary and/or key secondary hypotheses, or the statistical methods related to those hypotheses, then the protocol will be amended (consistent with ICH Guideline E-9). Changes to exploratory or other non-confirmatory analyses made after the protocol has been finalized, but prior to final database lock, will be documented in a supplemental SAP (sSAP) and referenced in the Clinical Study Report (CSR) for the study. There will be a separate PK analysis plan. Post hoc exploratory analyses will be clearly identified in the CSR.

8.1 Statistical Analysis Plan Summary

Key elements of the statistical analysis plan are summarized below. The comprehensive plan is provided in Sections 8.2 through 8.12.

Study Design Overview	A Phase II Study of Pembrolizumab Monotherapy in Third Line, Previously Treated Subjects with Advanced/Metastatic Adenocarcinoma or Squamous Cell Carcinoma of the Esophagus or Advanced/Metastatic Siewert Type I Adenocarcinoma of the Esophagogastric Junction (KEYNOTE – 180)
Treatment Assignment	This is a single-arm open-label study.
Analysis Populations	All Subjects as Treated (ASaT)
Primary Endpoint(s)	ORR based on RECIST 1.1 assessed by central imaging vendor
Statistical Methods for Key Efficacy Analyses	95% CI for ORR will be calculated using the exact binomial distribution.
Statistical Methods for Key Safety Analyses	Count and percentage of AE will be provided.
Multiplicity	Not applicable since this is an estimation study.
Sample Size	The planned sample size is approximately 100 subjects. The primary objective of the study is to estimate ORR in all subjects and in subjects whose tumors are classified as GEP intermediate or high and subjects whose tumors are classified as GEP high. Section 8.7 provides the precision of the ORR estimates.

8.2 Responsibility for Analyses/In-House Blinding

The statistical analysis of the data obtained from this study will be the responsibility of the Clinical Biostatistics department of the SPONSOR.

This trial is being conducted as an open-label study, ie, subjects, investigators, and SPONSOR personnel will be aware of subject treatment.

The Clinical Biostatistics department will generate the allocation schedule.

8.3 Estimation

Objectives and estimations of the study are stated in Section 3.0.

8.4 Analysis Endpoints

8.4.1 Efficacy Endpoints

8.4.1.1 Primary Efficacy Endpoint

- **Objective response rate (ORR) - RECIST 1.1 assessed by central imaging vendor**

Objective response rate is defined as the proportion of the subjects in the analysis population who have a complete response (CR) or partial response (PR). Responses are based upon central imaging vendor assessments per RECIST 1.1.

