Docetaxel, paclitaxel, and irinotecan are included as options for second-line therapy for patients with locally advanced or metastatic disease. Other regimens included in the guidelines for patients with locally advanced or metastatic disease are derived from the gastric adenocarcinoma phase III trials that have included patients with lower esophageal and/or EGJ cancer. The use of gefitinib as a second-line treatment for unselected patients does not improve overall survival [42]. There are no standard guidelines for third-line treatment of patients with esophageal cancer as the efficacy of chemotherapy is expected to be very poor in this setting (<5%). In addition, patient PS frequently declines at this stage and patients are managed by addressing symptoms from tumor burden.

KEYNOTE-028, a nonrandomized, multicohort, Phase 1b trial of pembrolizumab for PD-L1⁺ advanced solid tumors includes esophageal cancer patients. Key eligibility criteria for this cohort included SCC or adenocarcinoma of the esophagus or EGJ junction, measurable disease, PD-L1 expression in ≥1% of cells in tumor nests or PD-L1⁺ stromal bands determined centrally by IHC, failure of standard therapy, ECOG PS 0-1, and no autoimmune disease. Pembrolizumab 10 mg/kg is being given every 2 weeks for up to 2 years or until confirmed progression. Of the 90 pts with esophageal cancer who were screened, 37 (44.6%)

had PD-L1⁺ tumors. Of the 23 patients treated between Mar and Dec 2014, 83% were men and median age was 65 years. Histology was squamous in 17 pts (73.9%), adenocarcinoma in 5 pts (21.7%), and mucoepidermoid in 1 patient (4.3%). Eighty-seven percent of pts received ≥ 2 prior therapies for metastatic disease; all pts received ≥ 1 platinum-based therapy. Nine patients (39.1%) experienced drug-related adverse events (DRAEs), including 4 (17.4%) who experienced Grade 3 DRAEs. There were no Grade 4 DRAEs, and no pts died or discontinued due to a DRAE. Tumor shrinkage was seen in 52% of patients and ORR was 30.4% (n = 7; 5 squamous (29.4%) and 2 adenocarcinoma (40.0%)); best response was stable disease (SD) in 13% (n = 3; 2 squamous and 1 adenocarcinoma) and progressive disease in 59% (n = 13). Six patients still remain on therapy. Median time to response is 16 weeks (Range: 7.9-36.0 weeks) and median duration of response is 40.0 weeks (Range: 0.1+ to 40.0 weeks) for the patients in the esophageal cohort.

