7.1.4.1.2 Tumor Imaging During the Trial

The first on study imaging assessment should be performed at 9 weeks (63 days \pm 7 days) from the date of allocation. Subsequent tumor imaging should be performed Q9W (63 days \pm 7 days) or more frequently if clinically indicated. Imaging timing should follow calendar days should not be adjusted for delays in cycle starts. Imaging should continue to be performed until disease progression (unless site investigator elects to continue treatment and follow irRECIST), the start of new anti-cancer treatment, withdrawal of consent, death, or notification by the SPONSOR, whichever occurs first. All supplemental imaging must be submitted to the central imaging vendor.

Per RECIST 1.1, partial or complete response should be confirmed by a repeat tumor imaging assessment not less than 4 weeks from the date the response was first documented. The tumor imaging for confirmation of response may be performed at the earliest 4 weeks after the first indication of response, or at the next scheduled tumor imaging (ie, 9 weeks later), whichever is clinically indicated. Subjects will then return to regular scheduled imaging Q9W, starting with the next scheduled imaging time point. Subjects who obtain a confirmation imaging scan do not need to undergo the next scheduled tumor imaging if it is < 4 weeks later; tumor imaging may resume at the subsequent scheduled imaging time point.

Per irRECIST (Section 7.1.4.1.6) disease progression should be confirmed by the site at least 4 weeks after site-assessed 1st radiologic evidence of PD in clinically stable subjects. Subjects who have unconfirmed disease progression may continue on treatment at the discretion of the site investigator until progression is confirmed by the site provided they have met the conditions detailed in Section 7.1.4.1.6. Subjects who obtain a confirmation scan do not need to undergo the next scheduled tumor imaging if it is < 4 weeks later; tumor imaging may resume at the subsequent scheduled imaging time point if clinically stable.

Subjects who have confirmed disease progression as assessed by the site will discontinue the treatment. Exception is detailed in Section 7.1.4.1.6.

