7.1.4.1.5 RECIST 1.1 Assessment of Disease

RECIST 1.1 will be applied by the central imaging vendor as the primary measure for assessment of tumor response, date of disease progression, and as a basis for all protocol guidelines related to disease status (eg, discontinuation of study therapy).

7.1.4.1.6 irRECIST Assessment of Disease

irRECIST is RECIST 1.1 adapted as described below to account for the unique tumor response seen with immunotherapeutic drugs. irRECIST will be used by site investigator/local radiology review to assess tumor response and progression, and make treatment decisions. This data will be collected in the clinical database. Treatment efficacy based on irRECIST as assessed by central imaging vendor review will be evaluated retrospectively.

When feasible, subjects should not be discontinued until progression is confirmed by the local site investigator/radiology assessment. This allowance to continue treatment despite initial radiologic progressive disease (PD) takes into account the observation that some subjects can have a transient tumor flare in the first few months after the start of immunotherapy, and then experience subsequent disease response. Subjects that are deemed clinically unstable are not required to have repeat tumor imaging for confirmation of PD. Tumor flare includes any of the following scenarios:

- Worsening of existing target lesion(s)
- Worsening of existing non-target lesion(s)
- Development of new lesion(s)

In subjects who have shown initial evidence of radiological PD by RECIST 1.1 as determined by the site, it is at the discretion of the PI whether to continue a subject on study treatment until repeat imaging is obtained (using irRECIST for subject management, see [Table 6](#) and [Figure 2](#)). This clinical judgment decision by the site investigator should be based on the subject's overall clinical condition, including performance status, clinical symptoms, and laboratory data. Subjects may receive study treatment and tumor assessment should be repeated ≥ 4 weeks later in order to confirm PD by irRECIST per site assessment. Clinical stability is defined as the following:

- 1) Absence of symptoms and signs indicating clinically significant progression of disease, including worsening of laboratory values
- 2) No decline in ECOG performance status
- 3) Absence of rapid progression of disease

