8.6 Statistical Methods

8.6.1 Statistical Methods for Efficacy Analyses

This section describes the statistical methods that address the primary and secondary objectives.

For the primary efficacy endpoint of ORR, the point estimate and 95% confidence interval will be provided using exact binomial method proposed by Clopper and Pearson (1934)[47]. Subjects in the primary analysis population (ASaT) without ORR data will be counted as non-responder.

For PFS, DOR and OS endpoints, Kaplan-Meier (KM) curves and median estimates from the KM curves will be provided as appropriate. The efficacy analysis is summarized in [Table 8](#).

Table 8 Analysis Strategy for Efficacy Variables

Endpoint/Variable[‡] (Description, Time Point)	Statistical Method	Analysis Population	Missing Data Approach
Primary Endpoint and Hypothesis			
ORR • RECIST 1.1, Central imaging vendor assessment	Exact method based on binomial distribution	ASaT • All subjects • Subjects whose tumors are classified as GEP intermediate or high • Subjects whose tumors are classified as GEP high	Subjects with missing data are considered non-responders
Secondary Endpoints			
DOR • RECIST 1.1, Central imaging vendor assessment	Summary statistics using Kaplan-Meier method	All responders	Non-responders are excluded from analysis
PFS • RECIST 1.1, Central imaging vendor assessment	Summary statistics using Kaplan-Meier method	ASaT	Censored at last assessment
OS	Summary statistics using Kaplan-Meier method	ASaT	Censored at last known alive date

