3.6 Statistical Methods

3.6.1 Statistical Methods for Efficacy Analyses

This section describes the statistical methods that address the primary and secondary objectives.

For the primary efficacy endpoint of ORR, the point estimate and 95% confidence interval will be provided using exact binomial method proposed by Clopper and Pearson (1934)[Ref. 5.4: 03RMKM]. Subjects in the primary analysis population (ASaT) without ORR data will be counted as non-responders.

For DCR, the point estimate, 95% confidence interval will be provided using the exact binomial method proposed by Clopper and Pearson (1934)[Ref. 5.4: 03RMKM]. Subjects in the analysis population (ASaT) with missing DCR data are considered as disease not under control.

For DOR, Kaplan-Meier (KM) curves and median estimates from the KM curves will be provided, as appropriate. Subjects who are alive, have not progressed, have not initiated new anti-cancer treatment, and have not been determined to be lost to follow-up are considered ongoing responders at the time of analysis. Censoring rules for DOR are summarized in [Table 1](#).

Table 1. Censoring Rules for DOR

Situation	Date of Progression or Censoring	Outcome
No progression nor death, no new anti-cancer therapy initiated	Last adequate disease assessment	Censored (non-event)
No progression nor death, new anti-cancer therapy initiated	Last adequate disease assessment before new anti-cancer therapy initiated	Censored (non-event)
≥ 2 consecutive missed disease assessments at any time prior to progression or death	Last adequate disease assessment prior to ≥ 2 missed adequate disease assessments	Censored (non-event)
Death or progression after ≤ 1 missed adequate disease assessments	PD or death	End of response (Event)

A missed disease assessment includes any assessment that is not obtained or is considered inadequate for evaluation of response. Subjects are considered to have an ongoing response if censored, alive, have not progressed, have not started a new anti-cancer therapy, have not had ≥ 2 consecutive missed disease assessments, and have not been determined to be lost to follow-up.

For PFS and OS endpoints, Kaplan-Meier (KM) curves and median estimates from the KM curves will be provided, as appropriate. The censoring rules for PFS are summarized in [Table 2](#). The efficacy analysis is summarized in [Table 3](#). The secondary and exploratory endpoints may be analyzed by populations as appropriate.

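### Does leaving the word confirmed out of the primary ORR definition let single-scan responses count?

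*Combined protocol and SAP*

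**What the plan says.** The primary endpoint in protocol section 8.4.1.1 is "the proportion of the subjects in the analysis population who have a complete response (CR) or partial response (PR", and its next sentence bases responses on the central vendor's RECIST 1.1 assessments. sSAP 3.4.1.1 repeats this and adds that the central read is blinded. Neither text says confirmed, and neither points to the imaging section.

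Section 7.1.4.1.2 (Tumor Imaging During the Trial) states that, under RECIST 1.1, "partial or complete response should be confirmed by a repeat tumor imaging assessment not less than 4 weeks" after it is first seen. Section 7.1.4.1.5 states that "RECIST 1.1 will be applied by the central imaging vendor as the primary measure for assessment of tumor response".

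For missing data, sSAP 3.6.1 says "Subjects in the primary analysis population (ASaT) without ORR data will be counted as non-responders", and protocol Table 8 in section 8.6.1 says "Subjects with missing data are considered non-responders". The sSAP definition of disease control rate (3.4.1.2) does require its CR or PR component to be confirmed. DOR runs from the first CR or PR and is analysed in responders only. Responders without progression, new therapy or loss to follow-up are "considered ongoing responders at the time of analysis" (sSAP 3.6.1).

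**The concern.** ORR is the only primary endpoint, in one arm, reported for three populations. Who counts as a responder therefore determines the main result. Taken alone, the definition would accept a PR seen on one scan. The missing-data rules would not remove a PR followed by PD at the next scan, since nothing is missing. A first PR on the last scan before the data cut could stay in the DOR curve with a duration of about one day.

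The background section seems to show this happening. For the earlier phase 1b esophageal cohort it reports "Tumor shrinkage was seen in 52% of patients and ORR was 30.4" per cent (7 responders among 23 treated), and "median duration of response is 40.0 weeks (Range: 0.1+ to 40.0 weeks". A duration of 0.1 weeks leaves no room for a confirming scan 4 weeks later. If single-scan responses were counted here too, ORR would be overstated against a confirmed rate. If they were not, this trial's ORR would not be like-for-like with the 30.4%.

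**Working it through.** **1. The texts side by side.** Section 8.4.1.1 names the criteria (central, RECIST 1.1). Section 7.1.4.1.2 says what those criteria ask for a CR or PR in this trial (a repeat scan at least 4 weeks later). Section 7.1.4.1.5 makes the central RECIST 1.1 read the primary measure of response. Together they give confirmed response. The DCR definition agrees, since its CR/PR component comes from the same central read and is confirmed.

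**2. Three possible courses under the two readings.**

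| Central read | Confirmed reading | Single-scan reading |
|---|---|---|
| PR, then PR or better at least 4 weeks later | responder | responder |
| PR, repeat scan missing or pending at the cut | non-responder | responder, DOR censored at about one day |
| PR, then PD at the next scheduled scan | non-responder | responder, DOR about 9 weeks |

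The last two rows cause trouble only if an unconfirmed PR has already been accepted as a response. The ongoing-responder sentence and sSAP Table 1 act after response status is fixed; they do not set it. The same holds for the worry that an ORR responder might fall outside DCR: on the confirmed reading, that subject is not an ORR responder.

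**3. The plan's own figures.** The exact 95% limits are the 0.025 quantile of Beta(x, n − x + 1) and the 0.975 quantile of Beta(x + 1, n − x). These reproduce all 11 rows of protocol Tables 9 to 11, for example 17/100: 10.2 to 25.8; 35/100: 25.7 to 45.2; 21/60: 23.1 to 48.4; 14/40: 20.6 to 51.7.

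**4. The earlier cohort.** 7/23 = 30.4% (13.2 to 52.9). A printed 0.1 weeks covers 0.05 × 7 = 0.35 to 0.15 × 7 = 1.05 days, against 4 × 7 = 28 days for confirmation. If exactly one of the seven was unconfirmed, 6/23 = 26.1% (10.2 to 48.4), which is 30.4 − 26.1 = 4.3 points lower. One in seven is 14.3%, with an exact interval of 0.4 to 57.9%, so it cannot predict the unconfirmed share in this trial.

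**5. Size here if single-scan responses did count.** The documents give no confirmation rate, so the shares below are assumptions.

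- One in seven unconfirmed (multiply by 6/7): 35/100 becomes 30/100 (21.2 to 40.0), 21/60 becomes 18/60 (18.8 to 43.2), 14/40 becomes 12/40 (16.6 to 46.5). Each is 5 points lower and inside the interval it started from.
- 10% to 30% unconfirmed: 30/100 (21.2 to 40.0) becomes 30 × 0.9 = 27 (18.6 to 36.8) to 30 × 0.7 = 21 (13.5 to 30.3). At the far end, 21% lies just below the starting lower limit of 21.2%.

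The difference between the two readings could therefore be material. The conclusion has to rest on which reading the text supports, not on the shift being small.

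**The case for a change.** The strongest case is textual. These documents do write confirmed where they want it: for DCR, for irRECIST progression in sSAP 3.4.1.3, and for stopping after CR in section 2.1. Its absence from the primary endpoint could look deliberate. Section 7.1.4.1.2 is an instruction about scans, worded as should, and does not say how an unconfirmed PR is classed. The sSAP revised the DOR definition without adding the word. Two analysts could in principle report different ORRs from the same scans.

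Part of this stands. The word and the cross-reference are missing, and the sSAP does not say whether an unconfirmed PR counts as stable disease for DCR. It does not follow that the two readings are equally supported. The imaging instruction is given explicitly as what RECIST 1.1 asks, and RECIST 1.1 is the standard the endpoint names. Nothing in either document says that a single scan suffices.

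The earlier cohort adds little. Section 4.2.1 does not give its response criteria, reader, confirmation rule, DOR start date or the meaning of the plus sign. If duration was timed from confirmation, 0.1+ weeks fits a confirmed response. Even under this trial's rules, sSAP Table 1 can censor a responder back to the first response when two consecutive scans are then missed. That paragraph also mixes denominators (13/23 is 56.5%, printed as 59%; 37/90 is 41.1%, printed as 44.6%), and six patients were still on therapy. Nor is 30.4% the only esophageal response rate cited: section 4.2.1 also gives 15% and 1/21 for paclitaxel. The cohort differs from this trial in larger ways (PD-L1-positive only, a different dose schedule, 73.9% squamous), so confirmation status is not what stands in the way of a like-for-like reading.

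**Conclusion.** No change to the plan follows. The definition leaves out a detail that the imaging sections supply, and an analyst working from the whole plan will count confirmed CR or PR and class an unconfirmed one as a non-response. On that reading the effect on ORR, and on who enters the DOR analysis, is zero. This assumes that section 7.1.4.1.2 governs the central read, as section 7.1.4.1.5 and the reference to RECIST 1.1 in 8.4.1.1 indicate. How an unconfirmed PR enters DCR remains unstated, but that affects one secondary endpoint.

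The study is estimation only, with no hypothesis test, threshold or interim analysis (sections 8.7 and 8.8), so no decision turns on the missing word. Adding it would be tidy, but 8.4.1.1 is protocol text and the edit would not be expected to move any reported figure. The possible unconfirmed response in the earlier cohort is a caution for anyone who sets this trial's ORR beside 30.4%; it is not a fault in this trial's endpoint.
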